The study-specific assessments are detailed in this section and outlined in the Appendix 3 Study Calendar. Screening assessments must be performed within 21 days prior to the first treatment with investigational product. Any results falling outside of the reference ranges may be repeated at the discretion of the investigator. All study visit procedures are allowed a window of ± 7 days unless otherwise noted. Treatment or visit delays for public holidays or weather conditions do not constitute a protocol violation.

A written, signed, informed consent form (ICF) must be obtained before any study-specific assessments are initiated. A signed copy of the signed ICF will be given to the subject and a copy will be filed in the medical record. The original will be kept on file with the study records. All patients who are consented will be entered in the Providence Brain and Spine Institute's password protected clinical trial management system (CTMS), Velos. Velos will also be used by the study sites as an electronic data capturing system to enter study data.

Pretreatment Period**Subject Recruitment & Screening**

Potential subjects will be recruited from the investigators' and subinvestigators' clinical practices. Every effort will be made to preserve subject confidentiality according to each site's policies and limit the use of protected health information in accordance with the requirements of the Health Insurance Portability and Accountability Act of 1996 (HIPAA). The study sites will also make efforts to recruit and retain women and members of minority groups in order to reflect the composition of the adult U.S. population as closely as possible with regard to age, gender, ethnicity and race.

Pre-Study

Prospective participants must have had a contrast-enhanced MRI post-tumor resection procedure. If the subject had a biopsy alone without resection, a cranial CT may be used

instead of a MRI, provided they had a preoperative MRI scan within 14 days of biopsy. Screening can occur after this post-operative imaging is completed.

1. Screening can occur after this post-operative MRI.
2. Have had tumor resection surgery at day -42 to day -21 or stereotactic biopsy at day -14 to day -28. Patients who were only able to have a biopsy safely and not full resection have a shorter window from procedure date to Day 1.

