- Patient imaging will be sent to Novocure for treatment planning using NovoTAL™ and determining the appropriate transducer array layout. This must be done within 14 days prior to Day 1 (typically requires 5 business days). Patients will be trained by the investigator or the device specialist on the placement of the arrays.
- Electrocardiogram (ECG) at screening only. To be collected and read by cardiology department.
- Documentation of seizure frequency along with type of seizure (generalized or partial) and/or headache severity and frequency
- Scheduling of radiation oncology initial clinical visit and planning for therapy, if not already completed at the time of screening. Radiation oncology clinical visit is per standard of care.
- Adverse events to be assessed beginning after time of informed consent
- Eligibility assessment

Study Enrollment

Once the subject has been scheduled for radiation oncology planning and all eligibility criteria are met, the subject will be able to move to the Day 1 clinic visit for enrollment into the trial.

- RT and TMZ are to be initiated after the clinic visit. **TTField therapy can be initiated either that same day or no more than 7 days from the Day 1 clinic visit.**
- For this purpose, the staff will also coordinate with Novocure for a Device Support Specialist (DSS) trained by Novocure to initiate treatment either in clinic or at the subject's home within the above time frame.

[figure not shown]
Treatment Period

Study Procedures, Trimodal therapy phase – Day 1 of treatment is marked by the Day 1 clinic visit, just prior to initiation of trimodal therapy.

- The following guidelines should be observed regarding the **sequence of initiating trimodal therapy:**
 - TTField therapy can start as soon as the same day as the day 1 clinic visit, no more than 7 days after the day 1 visit, and up to 14 days before RT/TMZ initiation.

- **TTField therapy must be initiated prior to RT simulation and mask preparation.**
 - Preferably, patients would have the TTF initiated for a few days **prior to** radiation therapy to adjust for user errors and patient issues.
- RT should be initiated no more than 14 days after the day 1 visit. Subjects will receive radiation therapy within 4-6 weeks of their surgical resection or 2-4 weeks of their biopsy for the purpose of ensuring proper wound-healing.

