- TMZ treatment should also be coordinated to start on the first day of RT, but starting no more than 7 days after start of RT is acceptable and will not be recorded as a treatment delay. TMZ may start within 24 hours before RT, per investigator discretion.

Sequence of Starting Trimodal Therapy

^A TTField therapy can start as soon as the same day as the day 1 clinic visit, no more than 7 days after the day 1 visit (Day 1 to Day 8), and up to 14 days before RT/TMZ initiation.

^B TTField therapy must be initiated prior to RT simulation and mask preparation. Preferably, patients would have the TTF initiated for a few days prior to radiation therapy to adjust for user errors and patient issues.

^C RT should be initiated no more than 14 days after the day 1 visit (by Day 15).

^D Subjects will receive radiation therapy within 4-6 weeks of their surgical resection or 2-4 weeks of their biopsy for the purpose of ensuring proper wound-healing.

^E TMZ treatment should also be coordinated to start on the first day of RT, but starting no more than 7 days after start of RT is acceptable and will not be recorded as a treatment delay (by Day 22). TMZ may start within 24 hours before RT, per investigator discretion.

During this phase, study procedures should be completed +/- 7 days from the Day specified unless otherwise noted.

During this phase, patients will undergo weekly skin checks by radiation oncology or neuro-oncology. Transducer arrays must be off the skin in order to perform a careful examination of the skin for toxicity. The patient and physician needs to time the changing of transducer arrays such that the arrays are not worn during weekly visits. The same practice applies to skin checks after the trimodal therapy phase and during adjuvant treatment per the standard of care.

Trimodal therapy, Day 1 (21-42 days from surgery or 14-28 days from stereotactic biopsy)

The following procedures are to be completed on Day 1 prior to TTField initiation:

- Vital signs: weight, temperature, pulse, respiration rate, and resting blood pressure.
- Physical examination including neurologic exam, head and neck exam, and scalp exam to evaluate surgical healing and contraindications to radiation and TTField therapy.
- Adverse event assessment
- Concomitant medication review
- KPS (performance) assessment
- Complete blood count (CBC) with differential and platelet count (if completed for screening within 14 days of Day 1, does not need to be repeated)

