7. SUBJECT ASSESSMENTS FOR SAFETY AND EFFICACY

The study procedure calendar for this study is provided in **Appendix 3**.

a) Evaluation of Safety and Tolerability**Dose Limiting Toxicity**

Dose limiting toxicities (DLTs) are defined as any severe or life-threatening treatment-related toxicity that precludes the use of a specified dose of any of the study treatments (TTFields, temozolomide, radiation) including continued use of Optune TTFields device at the standard treatment levels and schedule set out by prior studies. This study will prioritize preserving the standard of care for glioblastoma using approved dosing and radiation of temozolomide and radiation.

Toxicities will be graded according to the CTCAE (Version 5.0) scale. If multiple toxicities are seen, the presence of DLT should be based on the most severe toxicity experienced. Dose-limiting toxicities will be defined as any of the following events which occur during the experimental trimodal therapy with TTFields is added concurrently to radiation and temozolomide therapy or during the 8 weeks after RT is completed, and are considered by the investigator to be attributable to TTFields or the combination of TTFields with radiation and/or temozolomide:

- Any Grade > 3 thrombocytopenia, and Grade 4 anemia and neutropenia.
- Any nonhematologic Grade > 3 toxicity (including nausea, vomiting, or diarrhea), excluding alopecia.

- Any Grade 3-4 radiation-induced skin changes that persist for greater than 7 days and does not improve with management recommendations as outlined in toxicity management.
- Any adverse effect deemed by the investigator, patient's primary neuro-oncologist, or radiation oncologist to be life threatening in nature.

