Appendix 3 Study Calendar

Procedure/Visit	Pre-Study	Study Period (extends 8 weeks post RT/TMZ for DLT monitoring)					Long-Term Follow-up		Any time during Study Period	Any time during Study Period
	Pre-Consent	Screening	Trimodal Therapy (6-7 weeks)	Post RT/TMZ (4 weeks)	Adjuvant TMZ Therapy (Cycles are 28 days each)			Adjuvant TMZ Therapy Cycles 3-6 and beyond, if applicable	Maintenance TTField Therapy ^L	Any time during Study Period
		Day -21 to 0	Day 1	Day 8 +7 days; Day 15, 22, 29, 36, 43 ±7 days for each	Day 64 ±7 days	Cycle 1 (First cycle 1 begins on Day 78 ±5 days)	Cycle 2 (First cycle 2 begins on Day 106 ±5 days)	Minimum of 4 additional cycles		
Tumor Resection or Biopsy	X ^{DD}									
Informed Consent		X								
Demographics		X ^I								
Eligibility Review		X	X							
Medical History		X								
Treatment History/Toxicity Assessment		X ^M								
Disease Assessment/Extent of Measurable Disease		X ^D			X ^P	X ^{P, EE}	-----X ^{P, CC} -----			
Vital Signs ^Q		X ^A	X		X	X				X ^{GG}
Physical Exam		X ^B	X ^{B, H}		X ^K	X ^K	X ^K			X ^{GG}
Neuro Exam		X		X ^K						X ^{GG}
KPS		X	X		X	X	X			X ^{GG}
Objective Response					X	X ^{EE}	-----X ^{CC} -----			X ^{GG}
CBC w/diff & Platelet Count		X	X ^U	X	X	X	X			X ^{GG}
Blood Chemistry ^S		X	X ^U		X	X	X			X ^{GG}
Confirm MGMT Testing		X ^R								
Documentation of IDH status		X ^R								
Coagulation Assessment ^T		X								
Serum or Urine Preg Test		X								
ECG		X ^W								
MRI of the Brain w/wo Contrast ^O	X ^F				X ^{HH}					X ^{GG, HH}
Review of Imaging for Treatment Planning		X ^C								
Seizure & Headache Assessment ^I		X	X							
Radiation Oncology Planning		X								

Device Specialist			X ^G	X		X-----X-----				X ^{GG}	
TTField Compliance Review ^{FF}			X	X		X-----X-----		X-----X-----		X ^{GG}	X
TTField Therapy			X ^G	X	X	X	X	X-----X-----		X ^{GG}	
Radiation Therapy (RT)			X ^G	X ^{BB}						X ^{GG}	
Temozolomide (TMZ)			X ^G	X ^{BB}		X ^V	X			X ^{GG}	
Skin Exam			X	X ^{N, HH}	X ^{N, HH}	X ^{N, Y, HH}	X ^{N, Y, HH}			X ^{GG, HH}	
Con meds		X ^E			X-----X-----					X ^{GG}	X
Adverse Events ^{AA}				X-----X-----						X ^{GG}	X
Survival Documentation								X-----X ^Z -----			

A: To include height at screening.
B: Including neurologic exam, head exam, and neck exam.
C: Must be done within 14 days prior to Day 1.
D: At screening, to including documented pathology proven glioblastoma or gliosarcoma.
E: To include medications taken within 7 days of Day 1.

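### Windows of ±7 days on trimodal visits 7 days apart conflict with the weekly skin checks and allow up to 21 days between blood counts

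*Combined protocol and SAP*

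**What the plan says.** Section 6, Clinical Trial-Related Procedures, sets a study-wide default: "All study visit procedures are allowed a window of ± 7 days unless otherwise noted". The Treatment Period text repeats it for the trimodal phase: "During this phase, study procedures should be completed +/- 7 days from the Day specified unless otherwise noted". The individual headings for Days 15 to 43 print ±7 days again. The Day 8 heading prints no window, so the default applies to it. Appendix 3 reads differently for that visit: "Day 8 +7 days; Day 15, 22, 29, 36, 43 ±7 days for each".

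The frequency of skin exams is stated separately. Close to the window sentence, the Treatment Period text says "patients will undergo weekly skin checks by radiation oncology or neuro-oncology". The synopsis and the General Study Design text in Section 6 also call for weekly skin exams. CBC is listed at each of the six visits and in the Appendix 3 row, but nothing states a CBC frequency apart from those visits.

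Two sets of rules rely on these observations:

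- Section 7a counts as a DLT "Any Grade 3-4 radiation-induced skin changes that persist for greater than 7 days" and that also fail to improve with the recommended management. It has hematologic DLT grades as well.
- The temozolomide part of Treatment Modalities has neutrophil and platelet thresholds for the trimodal phase.

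On device start, Section 6 says "TTField therapy can start as soon as the same day as the day 1 clinic visit, no more than 7 days after the day 1", meaning the first clinic attendance.

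**The concern.** A visit window should absorb scheduling slippage without changing how often a patient is observed. Here the window on each side is as wide as the interval between visits, so the calendar no longer enforces the weekly spacing that it appears to show. A site or monitor working from Appendix 3 would find nothing out of window in a schedule with three weeks between assessments.

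This matters because DLT counts drive both safety stops in Section 6: 2 or more of the first 6 patients, and 5 or more of the first 15. An unobserved DLT can lower these counts but cannot raise them. If the true count is exactly at the limit, one missed event turns 2 of 6 into 1, or 5 of 15 into 4, and the study proceeds.

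**Working it through.** **Inputs.** Nominal visits are Days 8, 15, 22, 29, 36 and 43, so the spacing is 7 days (Section 6, Appendix 3). The half-width w is 7 days, except that Appendix 3 gives Day 8 only +7. The plan states no figure of its own to reproduce.

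**Windows.**

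| Visit | Window | Contains Day 15 | Contains Day 36 |
|---|---|---|---|
| Day 8 | 8–15 (Appendix 3); 1–15 (text) | yes | no |
| Day 15 | 8–22 | yes | no |
| Day 22 | 15–29 | yes | no |
| Day 29 | 22–36 | no | yes |
| Day 36 | 29–43 | no | yes |
| Day 43 | 36–50 | no | yes |

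**Fewest dates that meet all six windows.** One date cannot suffice, because the Day 8 window closes on Day 15 and the Day 43 window opens on Day 36. With two dates x < y, x must be 15 or earlier and y must be 36 or later. The Day 22 window (15–29) can then be met only by x = 15, and the Day 29 window (22–36) only by y = 36. Days 15 and 36 are therefore the only two-date solution, under either Day 8 window. They are 36 − 15 = 21 days apart.

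**Largest gap between adjacent visits.** The gap is 7 + 2w. With w = 7 this is 21 days, against 7 nominally. It does not depend on counting one attendance as several visits: six different dates (13, 14, 15, 36, 37, 38) are all in window and contain the same 21-day gap.

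**Effect of narrower windows.** Adjacent windows share a day when 2w ≥ 7, that is from w = 4 upward.

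| w (days) | Fewest dates | Largest adjacent gap (days) |
|---|---|---|
| 1, 2, 3 | 6 | 9, 11, 13 |
| 4, 5, 6 | 3 | 15, 17, 19 |
| 7 | 2 | 21 |

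**What this means for CBC.** Section 6 lets RT start as late as Day 15 with temozolomide on the same day, and lets both run to Day 49 + 7 = Day 56. Take that patient with CBCs on Days 15 and 36. The next required CBC is the Day 64 visit, which may fall on Day 64 + 7 = Day 71, and 71 − 36 = 35 days. Only one required CBC (Day 36) then falls after the first temozolomide day and before the course ends. The nominal calendar would give four (Days 22, 29, 36, 43). If RT and temozolomide start on Day 8, the comparison is two (Days 15, 36) against five (Days 15, 22, 29, 36, 43).

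**Day 8.** TTFields may start as late as Day 8. Under the text default the Day 8 exam may take place from Day 1, up to a week before the device is on. Under Appendix 3 it falls on Days 8–15, so it can precede device use only if both happen on Day 8 with the exam first.

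**The case against.** The strongest reply concerns skin. A reader might infer that the plan lets a patient have only two skin exams without any deviation. The documents do not support that: weekly skin checks are required in three places, and a two-exam schedule breaches them. What remains for skin is a contradiction between the weekly wording and the ±7-day windows.

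A reader might also infer that any Grade 3–4 skin change lasting 8 to 20 days, and so fitting between two exams, is a missed DLT. Section 7a also requires that the change does not improve with management, so duration alone does not meet the criterion. Once Grade 3–4 skin toxicity is seen during RT, Treatment Modalities calls for a break from TTFields and physician evaluation before resumption. Persistence would then not be judged only at the next calendar visit.

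For CBC, one can say that the text refers to the attendances as weekly visits, and that letting one blood draw serve several visits is inferred from silence. Both remarks are fair, but the six-date example shows that the 21-day gap needs no double counting.

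There are other safeguards. Patients attend for RT, change arrays two to three times a week, are asked to report notable skin toxicity, and may have unscheduled visits that include a CBC. These help most with visible or symptomatic events. Reporting relies on the patient and unscheduled visits are discretionary, so neither reliably finds an asymptomatic cytopenia.

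Finally, the Day 8 list of procedures presupposes that the device is already in use. This shows the intent, but the text default still permits an earlier exam.

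**Conclusion.** The point holds as an inconsistency in the monitoring schedule that should be corrected. The ±7-day windows cannot stand together with weekly skin checks. For CBC they permit up to 21 days between adjacent trimodal visits, so a transient cytopenia relevant to the hematologic DLT criteria or the temozolomide thresholds could go unseen. The Day 8 window differs between the text and Appendix 3.

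This is the worst case that the windows permit; the nominal schedule is weekly. It rests on finding no minimum or maximum interval between visits in the documents. The effect on the stopping rules has a known direction, towards proceeding, but no size can be given. That would need the frequency and duration of such events and how sites actually schedule, and a cytopenia counts as a DLT only if the investigator attributes it to TTFields or the combination. A reader might infer that the interim DLT counts are materially biased; the documents do not establish that.

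**What to change.** 1. Narrow the Day 8 to Day 43 windows to a width that does not overlap. The widest whole-day choice is ±3 days, which the protocol already uses for Day 22 of Cycle 1.
2. Require one skin exam and one CBC on a separate date in each week, and state the longest interval allowed between successive ones. The interval is needed because ±3 alone still permits 7 + 6 = 13 days (for example Day 5 to Day 18). A one-per-week rule adds nothing if the week is the ±3 window itself. If weeks run from the nominal day (Days 8–14, 15–21), the two rules together allow 7 + 3 = 10 days.
3. Give Day 8 the same window in the text and in Appendix 3, and require that skin exam to follow the start of TTFields.
4. Reconcile the windows with the weekly wording in the synopsis and Section 6 and with the persistence criterion in Section 7a, including how onset and resolution are dated when they fall between exams.

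The cost is a wording change to the protocol and calendar, plus somewhat more out-of-window deviations. That burden should be small, because patients attend for RT through most of this period.

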- Blood chemistry assessment, including (if completed for screening within 14 days of Day 1, does not need to be repeated):
 - Alkaline phosphatase, aspartate aminotransferase/alanine aminotransferase (ALT/AST), total bilirubin, calcium, blood urea nitrogen (BUN), creatinine, total protein, albumin, fasting glucose, potassium, sodium, chloride, bicarbonate
- Documentation of seizure frequency along with type of seizure (generalized or partial) and/or headache severity and frequency.
- Eligibility assessment
- Skin examination by investigator or subinvestigator

When the above procedures are completed, TTField therapy may be initiated:

- TTField therapy (see treatment modalities for detailed description of treatment and parameters) will be initiated by the investigator by calling the device support specialist to confirm the patient is ready. The Device Support Specialist (DSS) will visit the patient in their home or in the clinic and initiate treatment with TTField therapy (Accounting for scheduling, treatment initiation within 7 days from the Day 1 visit is acceptable and will not be marked as treatment delay).

Day 8 of Trimodal therapy

- Skin examination by investigator or subinvestigator in Radiation Oncology or Neuro-Oncology (document attribution, grade of toxicity, and if there is apparent correlation with the ceramic disc or adhesive gel on the transducer arrays). Treatment of mild skin toxicity as appropriate. If there are concerns of worsening skin toxicity, treatment break from Optune or consider referral to dermatologist for specialist evaluation (transducer arrays will need to be removed/replaced for exam).
- Complete blood count (CBC) with differential and platelet count
- Adverse event assessment

- Concomitant medication review
- Continuation of TTField Therapy
- Initiate radiation therapy in accordance with standard of care as detailed under treatment modalities.
- Initiate daily TMZ chemotherapy ideally on the same day as radiation in accordance with standard of care as detailed under treatment modalities. TMZ initiation up to 7 days after start of RT is permissible and will not be deemed a deviation.

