Day 36 (± 7 days)

- Skin examination by investigator or subinvestigator in Radiation Oncology or Neuro-Oncology (document attribution, grade of toxicity, and if there is apparent correlation with the ceramic disc or adhesive gel on the transducer arrays). Treatment of mild skin toxicity as appropriate. If there are concerns of worsening skin toxicity, referral to dermatologist for specialist evaluation (transducer arrays will need to be removed/replaced for exam).
- Complete blood count (CBC) with differential and platelet count
- Adverse event assessment
- Concomitant medication review
- Continuation of TTField Therapy
- Continuation of RT
- Continuation of TMZ therapy

Day 43 (± 7 days) Final week of Trimodal therapy

- Skin examination by investigator or subinvestigator in Radiation Oncology or Neuro-Oncology (document attribution, grade of toxicity, and if there is apparent correlation with the ceramic disc or adhesive gel on the transducer arrays). Treatment of mild skin toxicity as appropriate. If there are concerns of worsening skin toxicity, referral to

dermatologist for specialist evaluation (transducer arrays will need to be removed/replaced for exam).

- Neurological examination by investigator or subinvestigator in Radiation oncology or Neuro-oncology.
- Complete blood count (CBC) with differential and platelet count
- Adverse event assessment
- Concomitant medication review
- Continuation of TTField Therapy
- Continuation of RT until Day 49 + 7 days, as clinically appropriate
- Continuation of TMZ therapy until Day 49 + 7 days, as clinically appropriate

Day 64 (± 7 days) Post initial chemoradiation continued DLT window

This is marked by continued TTField therapy alone for 4 weeks with the following procedures for continued monitoring of DLTs and TRAEs. One visit to be conducted in the middle of the 4 weeks with the following procedures.

- Vital signs: weight, temperature, pulse, respiration rate, and resting blood pressure.
- Skin examination by investigator or subinvestigator in Neuro-Oncology (document attribution, grade of toxicity, and if there is apparent correlation with the ceramic disc or adhesive gel on the transducer arrays). Treatment of mild skin toxicity as appropriate. If there are concerns of worsening skin toxicity, referral to dermatologist for specialist evaluation (transducer arrays will need to be removed/replaced for exam).
- Physical examination including neurologic exam, skin and scalp assessment.

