- Complete blood count (CBC) with differential and platelet count
- Adverse event assessment
- Concomitant medication review
- Continue TTField therapy

Study procedures, Adjuvant therapy phase and monitoring of delayed toxicities until 8 weeks after completion of trimodal therapy.

This would fall 4 weeks after completion of radiation therapy and marked by initiation of TMZ chemotherapy on a 5 out of 28-day cycle along with continued TTField therapy per the standard of care. MRIs are recommended every 2 months during temozolomide therapy. Day 1 of cycle 1 and cycle 2 are marked by continued treatment per the standard of care along with assessments for delayed TRAEs following trimodal therapy and continued DLT window (4 weeks and 8 weeks after completion of trimodal therapy).

Adjuvant TMZ therapy, Day 1 of Cycle 1 (Study Day 78 ± 5 days) with delayed toxicity monitoring.

- MRI of the brain with and without contrast (transducer arrays will need to be removed/replaced for imaging)
- Vital signs: weight, temperature, pulse, respiration rate, and resting blood pressure.
- Physical examination including neurologic exam, skin and scalp assessment.
- Skin examination by investigator or subinvestigator in Neuro-Oncology (document attribution, grade of toxicity, and if there is apparent correlation with the ceramic disc or adhesive gel on the transducer arrays). If there are concerns of worsening skin toxicity, referral to dermatologist for specialist evaluation (transducer arrays will need to be removed/replaced for exam).
- Adverse event assessment
- Concomitant medication review
- Documentation of disease assessment, clinical response or deterioration, status and extent of measurable disease on imaging
- Objective response assessment
- KPS (performance) assessment
- Complete blood count (CBC) with differential and platelet count
- Blood chemistry assessment, including:
 - Alkaline phosphatase, aspartate aminotransferase/alanine aminotransferase (ALT/AST), total bilirubin, calcium, blood urea nitrogen (BUN), creatinine, total protein, albumin, fasting glucose, potassium, sodium, chloride, bicarbonate
- Initiate Cycle 1, day 1 treatment of adjuvant TMZ on a 5 out of 28-day cycle as detailed under treatment modalities. Dosing will start at 150mg/m²/day for the first cycle and then increased if tolerated to 200mg/m²/day for all subsequent cycles.

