Subjects will receive TMZ chemotherapy as part of the trimodal therapy phase concurrently with radiation and TTF therapy. This will be administered orally by the subjects at a dose of 75mg/m² (of their body surface area) daily during radiation therapy (typically for 42 consecutive days including on weekends, up to 49 days is acceptable; to Day 49 + 7 days). Subjects will then discontinue the chemotherapy and have a 4-week break after radiation prior to resuming TMZ adjuvant therapy concurrent with TTF therapy alone. Doses will then be administered for 5 consecutive days out of a 28-day cycle. For the first cycle of adjuvant therapy, subjects will be dosed at 150mg/m²/day for 5 days out of 28 days in the first cycle, and increased if tolerated to 200mg/m²/day and continue that dose until the end of chemotherapy. The standard requirement is for 6 cycles of adjuvant treatment post-radiation but this may be extended per the judgment of the subject's treating clinician to no more than 12 cycles of adjuvant TMZ therapy. Please see package insert for full details. Expected and potential treatment-related acute adverse effects include: Nausea, fatigue, constipation, liver toxicity, myelosuppression resulting in thrombocytopenia, leukopenia (or neutropenia), anemia, or pancytopenia.

Initiation of PJP prophylaxis is recommended but each site will be given discretion to follow their institutional protocols.

Dose modifications during Trimodal therapy phase

ANC $\geq 500/\text{mm}^3$ but $< 1,500/\text{mm}^3$ **or** platelet count $\geq 10,000/\text{mm}^3$ but $< 100,000/\text{mm}^3$ **or** grade 2 nonhematologic toxicity (excludes alopecia, nausea/vomiting): Interrupt therapy

ANC $< 500/\text{mm}^3$ **or** platelet count $< 10,000/\text{mm}^3$ **or** grade 3/4 nonhematologic toxicity (excludes alopecia, nausea/vomiting): Discontinue therapy

Dose modifications during adjuvant therapy phase (concurrent with TTFields therapy only)

ANC $< 1,000/\text{mm}^3$, platelet count $< 50,000/\text{mm}^3$, or grade 3 nonhematologic toxicity (excludes alopecia, nausea/vomiting) during previous cycle: Decrease dose by 1 dose level (by $50 \text{ mg/m}^2/\text{day}$ for 5 days), unless dose has already been lowered to $100 \text{ mg/m}^2/\text{day}$, then discontinue therapy.

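### No liver chemistry is scheduled from Day 8 to Day 43, so the temozolomide hold-and-stop rule has no planned test for a silent liver rise

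*Combined protocol and SAP*

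**What the plan says.** The visit lists are in section 6, Clinical Trial-Related Procedures. Chemistry, including AST/ALT, alkaline phosphatase and bilirubin, is listed at screening and Day 1. The Day 1 panel is conditional: "Blood chemistry assessment, including (if completed for screening within 14 days of Day 1, does not need to be repeated". The lists for Days 8, 15, 22, 29, 36 and 43 each name one laboratory test, the CBC. The Day 64 list also names only the CBC. Chemistry returns at "Day 1 of Cycle 1 (Study Day 78 ± 5 days) with delayed toxicity monitoring" and again at Day 1 of Cycle 2.

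Daily TMZ is started nominally at the Day 8 visit and at the latest by Day 22. It is given "typically for 42 consecutive days including on weekends, up to 49 days is acceptable"; the Day 43 list has "Continuation of TMZ therapy until Day 49 + 7 days, as clinically appropriate".

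The TMZ part of Treatment Modalities lists these expected effects among others: "Nausea, fatigue, constipation, liver toxicity, myelosuppression resulting in thrombocytopenia". Its dose rule for the trimodal phase has two nonhematologic triggers: "grade 2 nonhematologic toxicity (excludes alopecia, nausea/vomiting): Interrupt therapy" and "grade 3/4 nonhematologic toxicity (excludes alopecia, nausea/vomiting): Discontinue therapy". For anything further it says "Please see package insert for full details".

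**The concern.** The dose rule has a hematologic half and a nonhematologic half. The first is fed by a scheduled CBC at every visit from Day 8 to Day 43. The second covers liver toxicity, which the protocol itself expects, but no liver test is scheduled while daily TMZ is being given.

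The adverse event assessment at each visit can pick up liver toxicity that causes symptoms. It cannot pick up a rise in AST, ALT or bilirubin without symptoms. A site that follows the schedule exactly could continue daily TMZ through a grade 2 or grade 3 laboratory rise that the rule says should hold or stop it. The stake is the safety of the individual patient.

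**Working it through.** There is no sample size or power figure to reproduce. The check compares the visit lists with the dose rule and counts days.

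**1. Scheduled laboratory tests, by the visit text**

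| Visit | CBC | Chemistry |
|---|---|---|
| Day 1 | yes, waivable | yes, waivable |
| Days 8, 15, 22, 29, 36, 43 | 6 of 6 | 0 of 6 |
| Day 64 ± 7 | yes | not listed |
| Cycle 1 Day 1 (Day 78 ± 5) | yes | yes |
| Cycle 1 Day 22 | yes | not listed |
| Cycle 2 Day 1 (Day 106 ± 5) | yes | yes |

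Appendix 3 agrees for Days 8 to 43: the CBC row is marked in that cell and the chemistry row is blank.

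**2. Daily TMZ period.** Nominal: Days 8 to 49, 49 − 8 + 1 = 42 doses. Extended to Day 56: 56 − 8 + 1 = 49 doses. Latest start (Day 22) with the latest stop (Day 56): 56 − 22 + 1 = 35 doses. A late start means that fewer of the six visits fall under dosing, but none of them has chemistry.

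**3. Gap between scheduled panels, by the visit text**
- Day 1 to Day 78: 78 − 1 = 77 days (72 to 82 with the ± 5-day window).
- Day 1 panel waived for a screening panel 14 days earlier: 1 − 14 = Day −13, and 78 + 13 = 91 days (86 to 96).
- Last dose to next panel: 78 − 49 = 29 days, or 78 − 56 = 22 days if TMZ runs to Day 56.

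**4. If Appendix 3 intends a panel at Day 64.** The earliest in-window date is 64 − 7 = Day 57. The last permitted TMZ day is 49 + 7 = Day 56. The panel would still come after the last dose. The gap from Day 1 would be 64 − 1 = 63 days, or 64 + 13 = 77 with the waiver.

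**5. Other lines that might supply a test**
- Section 4 mentions blood draws for toxicity during radiation but names no test.
- Section 7a says that laboratory assessments will be done to find other toxicities but names no analyte and no day.
- The unscheduled visit lists chemistry at the investigator's discretion, and a silent rise gives no reason to call one.
- The package-insert reference sets no test or day in this protocol.

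**6. With panels added at Day 22 and Day 43**
- Nominal intervals: 22 − 1 = 21 days and 43 − 22 = 21 days.
- Nominal doses: 14 before the Day 22 panel (Days 8 to 21), 21 between the panels (Days 22 to 42), and 7 from Day 43 to Day 49 (14 if to Day 56).
- The ± 7-day windows can lengthen this. A panel at Day 15 and the next at Day 50 are both in window, with 35 doses between them (Days 15 to 49). So 21 is a nominal figure, not a ceiling.
- Volume: 30 × 2 = 60 panels, or 30 × 3 = 90 if Day 64 is also new.

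**The case against.** The best defense is that this is a device trial in which TMZ is background treatment under established practice. Clinics may check liver function anyway, and leaving that to them is a defensible choice. Exclusion 11 already removes patients with AST or ALT above 3 times the upper limit of normal, or bilirubin above the limit. The documents give no rate of asymptomatic liver rise on concurrent TMZ, so the benefit cannot be quantified. The rule is a general nonhematologic rule, and the adverse event assessments do feed it. A Day 43 panel can change only about the last week of nominal dosing.

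Much of this stands, and it keeps the point modest. It does not close the gap. Baseline exclusion does not detect a rise during treatment, and none of the lines that mention laboratory work names a liver test or a day.

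Four stronger readings are tempting and are not supported:
- **Patients go unmonitored.** The documents show only that the trial schedules no panel. They do not show what local care does.
- **The adjuvant phase is better monitored for its dose.** Its panels fall on the first day of a cycle, and Day 22 of Cycle 1 has only a CBC. Both phases take chemistry at the start and blood counts during, so comparing cumulative doses shows nothing about monitoring within a phase.
- **Appendix 3 contradicts the visit text at Day 64.** The table is damaged in the available copy. The KPS row shows the same pattern as the chemistry row although the Day 64 text lists no KPS, and the MRI mark appears displaced.
- **The primary safety results are biased.** A DLT must be attributed to TTFields or its combination with the other treatments. Section 7 attributes adverse events to the device, and the device's expected effects include nothing hepatic. All recognized events of grade 3 and above are entered whatever their attribution.

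**Conclusion.** The point holds as a cheap improvement in patient safety. Chemistry is scheduled at 0 of 6 visits from Day 8 to Day 43, against 6 of 6 for the CBC. The nominal gap between panels is 77 days by the visit text, up to 91 with the Day 1 waiver, and the whole daily TMZ course falls inside it. Reading Day 64 as a chemistry visit shortens the gap but does not put a test within dosing.

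This rests on the visit lists as written, on the Day 56 limit for concurrent TMZ, and on the general laboratory statements not being a scheduled panel. How many patients would have a silent rise is unknown from the documents. No effect on the DLT rate, the stopping rules or the device-attributed adverse event rate is claimed.

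**What to change.** Add a non-fasting panel of AST, ALT, alkaline phosphatase, total bilirubin and creatinine to the blood draws that already take place at Day 22 and Day 43, in both the visit lists and Appendix 3. State in the Day 64 text whether chemistry is taken there; preferably it is.

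The cost is 60 extra panels for 30 patients, or at most 90 if Day 64 is also new. No visit is added, and leaving out glucose avoids fasting. The downside is that some TMZ doses will be held for grade 2 rises that would otherwise go unseen. The existing dose rule already requires those holds, but they pull against the aim in section 7a of preserving standard treatment.
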